## **5 Evaluation Tools**

## 5.1 Objective Outcomes

## 5.1.1 Radiographs and HHS

To assess radiographic stability, radiographs will be taken and collected in the Low AP Pelvis and Lateral views for the preoperative, 6-week, 3-6 months, 1-year, 2-year, 5-year, 7-year, and 10-year intervals.

The Low AP Pelvis view allows for observation of any conditions involving the sacral wings, iliac bones, ischium, pubis as well as the femoral head and neck. The Lateral view allows for evaluation of the entire hip joint as well as the femoral head, neck and proximal shaft. Suggested radiographic technique for the views required is included in **Appendix E**.

Radiographs will be evaluated by an independent reviewer throughout the course of the study. Radiographic analysis of the acetabular component will employ three zones (Zone 1-Zone 3) in the AP views. (15), (16) Numerous parameters will be reviewed by zone, including radiolucency and migration, in addition to overall cup/shell stability. Radiolucency in at least 50% of a zone and measuring at least 1 mm in width is defined as radiolucency present. Cases that present with migration of greater than 5 mm in any direction or at least 2 mm radiolucency in all zones will be considered radiographic failures.

Clinical outcomes will be evaluated via the HHS including pain, motion and function, preoperatively and at the 6-week, 1-year, 2-year, 5-year, 7-year and 10-year intervals.

## 5.2 Patient Reported Outcomes

Patient outcomes data will also be collected via patient questionnaires. During the preoperative, 6-week, 1-year, 2-year, 3-year, 4-year, 5-year, 7-year and 10-year follow-up visits, the VR-12, LEAS and EQ-5D are required. In addition, all subjects will complete a brief satisfaction questionnaire at the 6-week, 3-6 month, and annually through the 10-year follow-up interval when a HHS is not available.

## **6 Adverse Events**

## 6.1 Reporting of Adverse Events

The AE reporting requirements for this study are as follows:

- All AEs that meet the definition of serious and occur from intraoperative to 90 days postoperative
- All AEs related to the operative site, regardless of seriousness or time of occurrence

On postoperative functional evaluations, investigators and Study Coordinators (SC) will be prompted to question subjects as to whether they have seen a doctor for any reason, been hospitalized for any reason or have a current impediment to their function.

Additionally, SCs will be responsible for following up with the subjects regarding any questionable responses received on the Follow-up Questionnaire collected in lieu of the completion of a HHS at the 6-week through 10-year intervals. If it is determined upon this further investigation that a protocol-defined AE has occurred, the SC will be responsible for completing an AE eCRF, submitting the event to Stryker and reporting to the IRB as required.

The following decision tree facilitates identification of AEs for which reporting is required under this study protocol:

[figure not shown]

Figure 1. Adverse Event Decision Tree

General Physical Examination Findings

At screening for inclusion into the study, any clinically significant abnormality should be recorded

as a preexisting condition and reported on the Demographics eCRF. From the time of consent

forward, any new clinically significant findings or abnormalities that meet the definition of a

protocol defined AE must also be recorded and documented as an AE.

Adverse Event Reporting Period

The study period during which AEs must be reported is normally defined as the period from the

initiation of any study procedures to the end of the study treatment follow-up. The start of study

procedures is considered to be the point of consent. Any AEs that fit the protocol defined

reportable events must be reported from the time of consent until study completion.

At each contact with the subject, the investigator must seek information on AEs by specific

questioning and, as appropriate, by examination. Information on protocol defined AEs should be

recorded immediately in the source document and also in the appropriate AE module of the eCRF.

All clearly related signs, symptoms and abnormal diagnostic procedure results should be recorded

in the source document and grouped under one diagnosis, as appropriate. The clinical course of

each event should be followed until resolution or until it is determined at the end of the study that

the AE will not resolve.

All operative site events occurring at any time as well as all serious adverse events (SAEs)

occurring from the intraoperative timepoint to 90 days postoperative will be collected and

compared to published data. It is expected that the AE rates reported for the Trident II Acetabular

Shell will be comparable to those reported in the literature for other revision cementless

acetabular shells on the market.

6.2 General Adverse Event Definitions

Following is a list of general AE definitions. For the purposes of this study, only SAEs,

excluding elective procedures, as well as all AEs related to the operative site should be

reported.

Adverse Event

An **AE** is any untoward medical occurrence in a clinical investigation subject, which changes the

medical baseline of the subject. An AE can be an unfavorable and unintended sign, symptom or

CONFIDENTIAL

This material is the property of Stryker. Do not disclose or use except as authorized in writing by Stryker.

disease, whether or not related to the study device (AEs may also be referred to as complications). See **Section 6.1**, **Reporting of Adverse Events**, for the AE reporting requirements for this study.

#### Anticipated Adverse Event

An **anticipated AE** is an AE, of which the nature, severity or degree of incidence is known and identified in applicable product labeling, published literature or the study protocol. The list of anticipated events is provided in **Section 11**, **Risk/Benefit Assessment**.

#### Serious Adverse Event

A **SAE** meets one or more of the following definitions:

- Led to death
- Led to serious deterioration in the health of the subject, that either resulted in the following:
  - A life-threatening illness or injury
  - A permanent impairment of a body structure or a body function
  - o An in-patient or prolonged hospitalization
  - A medical or surgical intervention to prevent life-threatening illness or injury or permanent impairment to a body structure or a body function
- Led to foetal distress, foetal death or a congenital abnormality or birth defect

#### Adverse Device Effect

An **adverse device effect** (ADE) is a negative change in the subject's health that may have been caused by, or associated with, the use of the device.

#### Unanticipated Adverse Device Effect

An **unanticipated adverse device effect** (UADE) is any serious adverse effect on health, safety or any life-threatening problem or death caused by, or associated with, a device if that effect is a problem or death not previously identified in nature, severity or degree of incidence, or any other unanticipated serious problem associated with a device and related to the rights, safety or welfare of subjects.

#### 6.3 Study Sponsor Notification by Investigator

Of reportable AEs, certain events must be submitted to Stryker within 24 hours for timely notification.

#### AEs that require time sensitive reporting:

An AE should be reported to Stryker Clinical Research either by telephone/fax/email within 24 hours of the site becoming aware of the event if any of the following apply:

- The AE occurs intraoperatively or is related to the surgical procedure.
- The AE is considered by the investigator to be device related or if the investigator is uncertain regarding the device related assessment;
- The AE required a reoperation of the study hip or a revision of any study hip components.

At the time of the initial report, the following information should be provided:

Subject number	
 
Whether study treatment was
 

A description of the event	discontinued
Date of onset	
 
Investigator assessment of the
 

Current status	association between the event and
	the study treatment

An AE eCRF for an AE meeting the criteria above should be completed within 24 hours of the investigative center's awareness, and the de-identified source documentation should be submitted to Stryker within 24 hours of the investigative center's awareness. These reports will be evaluated by Stryker to determine if a Product Inquiry (PI) is required.

It is recommended that all other reportable AEs are submitted through eCRF entry within 2 weeks.

## 6.3.1 Institutional Review Board Notification by Investigator

Reports of AEs (including follow-up information) must be submitted to the IRB according to each IRB's specific reporting requirements. Copies of each report and documentation of IRB notification and receipt will be kept with the investigator's study files.

#### 6.3.2 Device Retrieval Process

If the study device is removed for any reason, Stryker may retrieve the Trident II Acetabular Shell and/or adjacent tissues for analysis to help characterize potential device-related complications. In the event that the Trident II Acetabular Shell is removed from a study subject, the procedure outlined in the Retrieved Implant Analysis Protocol (Appendix F) should be followed, as allowed by the patient consent, hospital and institution. In addition:

- 1. When revision of a study subject is scheduled, the SC should contact the Clinical Study Manager (CSM) or other Stryker Clinical Research personnel assigned to the project, as soon as possible.
- 2. Stryker Clinical Research will send a retrieval container to the SC.
- 3. After the device is explanted, the SC or an identified Stryker field representative will retrieve the device and place it in the retrieval container, following the instructions in **Appendix F**.
- 4. The SC, an identified field representative or Stryker Clinical Research will complete a PI.
- If not completed by Stryker Clinical Research, the PI should be faxed or emailed to Stryker Product Surveillance at [contact] or [contact], as well as to Stryker Clinical Research at [contact] or to the Clinical Research email addresses listed on the Sponsor Contact Sheet.
- The PI should be attached to the retrieval container and sent to Product Surveillance. A de-identified operative report should be included, when available.
- 7. Stryker Clinical Research will follow up with Product Surveillance to obtain a Pl
- 8. A summary of results will be provided to the investigator upon his/her request.

## 6.4 Recording of Adverse Events

All protocol defined AEs occurring during the study period must be recorded; this includes events that occur between visit intervals. The clinical course of each event should be followed until resolution or stabilization.

#### 6.5 Medical Monitoring

It is the responsibility of the investigator to oversee the safety of the study at his/her center. This safety monitoring will include careful assessment and appropriate reporting of AEs, as previously noted. Stryker will conduct formal investigations via the Product Surveillance Department of those AEs which are submitted through Stryker's PI System.

## 7 Data Management

#### 7.1 Database

Data will be collected at each center and entered into Stryker's Electronic Data Capture (EDC) system. The system can be accessed remotely by each investigative center and the data entered will be managed by Stryker. Subject data will be processed and monitored according to the protocol schedule by Stryker or Stryker representatives. Draft specifications to support eCRFs are provided in **Appendix G**.

Radiographic images will be collected by each center and uploaded into Stryker's medical imaging platform. This platform allows quick and compliant upload and review of medical images and data where they can be accessed by Stryker. The platform also enables secure sharing of documents with and issues queries to, participating sites. Quality control of the images will be managed by designated Stryker personnel. An independent reviewer will perform review of X-rays and transcribe measurements to Stryker radiographic evaluation forms. Draft specifications to support radiographic evaluation forms are provided in **Appendix H**.

## 7.2 Confidentiality

This study will comply with the 2002 HIPAA privacy rule. As such, Stryker will only collect that information which is necessary to support the objectives of the study. Stryker has a process to filter out identifying information in the data received during the course of the study. In the case that identifying information is inadvertently received, Stryker will redact and/or return the same in order to ensure no further disclosure. Study subjects will authorize Stryker and its affiliates to receive, retain and use their health information in support of the clinical study during the informed consent process. Should a subject choose to withdraw authorization, Stryker may use data collected prior to the withdrawal of authorization, as described in the patient consent.

#### 7.3 Source Documents

Source data include all information, original records of clinical findings, observations or other activities in a clinical study necessary for the reconstruction and evaluation of the study. Source data are contained in source documents. Examples of these original documents and data records include: hospital records, clinical and office charts, study worksheets, laboratory notes, memoranda, subject questionnaires, pharmacy dispensing records, recorded data from automated instruments, radiographs, subject files, and records kept at the pharmacy, at the laboratories and at medico-technical departments involved in the clinical study.

All data points collected during preoperative and follow-up visits must be documented in the subject's chart. This includes range of motion values, pain and function as well as AEs and additional comments. The informed consent process should also be documented in the patient chart. Monitors, defined further in **Section 9**, will be comparing the eCRFs against source documents for accuracy. The monitors will seek to draw a reference between each data point on the eCRF and the subject's chart. Thus, one cannot derive pain, ROM or function based on a chart note that reads "Patient doing well." Every effort should be made to ensure complete source documentation.

Centers are required to create a source documentation plan including any applicable source documentation worksheets prior to enrollment.

## 7.4 Electronic Case Report Forms

The study eCRFs are the primary data collection instrument for the study. All data requested on the eCRF must be documented. All missing data must be explained. It is recommended that eCRFs be completed and that any forms requiring signature are electronically signed by the investigator within 2 weeks of the evaluation date.

#### 7.5 Data Queries

If errors or omissions are noted by Stryker upon review of the data entered into the eCRFs, a data query will be sent to the center within the EDC system. Queries should be answered in a clear and comprehensible manner. If the clarification requires a change to study data, the personnel delegated to enter EDC data must update the data directly in the EDC system. The query will be closed upon an acceptable response. The investigative center will be required to reapply their electronic signature to the modified eCRF.

#### 7.6 Protocol Deviations

Any deviation from this protocol categorized as a 'Major Protocol Deviation' will be recorded by the Sponsor and must be reported to the investigational center's overseeing IRB according to their reporting procedures. Major protocol deviations for this study may include the following; this list may not be all-inclusive:

- Informed consent deviations, including but not limited to:
  - Study procedures performed prior to informed consent
  - Incorrect informed consent version used
- Patient enrolled does not meet the inclusion/exclusion criteria
- Protocol specified study component(s) not implanted
- Off label surgical approach
- Off label component usage
  - If the stem is not a Stryker device it must be revised to a compatible Stryker component or the patient will be censored

If the center anticipates a possible protocol deviation, the investigator or SC should contact Stryker for guidance.

#### 7.7 Records Retention

It is the investigator's responsibility to retain study essential documents for two years after the date of the final report, or in the case of non-compliance, two years after the date of investigative center termination. These documents should be retained for a longer period if required by an agreement with Stryker.

#### 8 Statistical Plan

## 8.1 Study Objectives

## 8.1.1 Primary Objective Analysis

The primary hypothesis to be tested will be that the success rate at five years postoperative with the Trident II Acetabular Shell is not worse than 95% with a non-inferiority margin of 5%. That is, the following hypothesis will be tested:

H0: Pt <= 95% - 5% HA: Pt >95 % - 5%

Here, Pt is the success rate at five years postoperative with the Trident II Acetabular Shell. Case success at five years is defined as no incidence of revision and removal of Trident II Acetabular Shell for aseptic loosening within five years.

A 90% two-sided confidence interval will be computed for the success rate at five years. If the lower bound of the confidence interval is greater than a 90% survival rate, then the non-inferiority hypothesis will be supported, that is the five-year success rate is non-inferior to 95% with a margin of 5%. If the lower bound of the confidence interval is greater than 95% then it is supported that the five-year success rate is superior to 95%.

The Kaplan-Meier survival curve of revision and removal of the Trident II Acetabular Shell for aseptic loosening will be displayed using SAS/PROC LIFETEST.

## 8.1.2 Secondary Objective Analyses

Radiographic stability will be tabulated for available visits.

The analysis for the additional data collection is in **8.4.1 Data Summary**.

## 8.2 Safety

## 8.2.1 Safety Parameters

Safety parameters include all protocol-defined adverse events as well as all-cause revision and/or removal of the Trident II Acetabular Shell. For details regarding protocol-defined adverse events, see **Section 6.1**.

#### 8.2.2 Safety Analyses

The frequency and percentage of all protocol-defined adverse events will be tabulated. All protocol-defined adverse events will be tabulated and 95% confidence interval will be presented. For details regarding protocol-defined adverse events, see **Section 6.1**.

The Kaplan-Meier survival curve of all cause of revision and removal of the Trident II Acetabular Shell at ten years postoperative will be displayed.

#### 8.3 Missing Data

No missing data will be imputed.

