## 8.4.2 Sample Size Justification

Based on the literature review, it is reasonable to have a reference value of 95% of success rate at five years, and a case success at five years is defined as no incidence of revision and removal of Trident II Acetabular Shell for aseptic loosening within the five-year follow-up period. With the expectation that the success rate of Trident II Acetabular Shell for aseptic loosening within five years will be 94.5%, 277 cases will be needed to have a power of 95% to detect that the 5-year success rate is non-inferior to 95% with a margin of 5% at 5% significance level. After factoring a 20% lost to follow-up rate, a total of 347 cases will be needed.

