#### 8.4.4 Analysis Population

**Per Protocol Population**: The study population for analysis will include all non-censored subjects who received the Trident II Acetabular Shell and are available for efficacy evaluation at the 5-year primary endpoint.

The primary and secondary efficacy analyses will be based on the per protocol population.

**Safety Population**: The safety population will include all non-censored subjects who received the Trident II Acetabular Shell.

The safety analysis will be based on the safety population.

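### The non-inferiority claim assumes that hips lost before five years loosen no more often than hips seen, and no planned analysis tests this

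*Combined protocol and SAP*

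**What the plan says.** - **Missing data (8.3).** The section is a single sentence: "No missing data will be imputed".
- **Analysis set (8.4.4).** The per-protocol population, used for the primary and secondary efficacy analyses, is limited to non-censored subjects who received the shell and "are available for efficacy evaluation at the 5-year primary endpoint". No second efficacy population is defined.
- **Loss allowance (8.4.2).** From 277 evaluable cases: "After factoring a 20% lost to follow-up rate, a total of 347 cases will be needed".
- **Test (8.1.1).** "A 90% two-sided confidence interval will be computed for the success rate at five years". The rule is: "If the lower bound of the confidence interval is greater than a 90% survival rate, then the non-inferiority hypothesis will be supported". The type of interval is not named. A Kaplan-Meier curve for this endpoint is to be displayed, but the section does not say that the tested interval comes from it.
- **Other relevant analysis (8.2.2).** A ten-year Kaplan-Meier curve of all-cause revision in the safety population is planned. It is descriptive and concerns a different endpoint.

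The plan contains no worst-case, tipping-point or all-implanted analysis of the primary endpoint.

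**The concern.** The trial compares one arm with a fixed 90% bound, so no control group shares the loss and offsets any bias. If hips that drop out fail more often than hips that stay, the observed success rate is too high, and the error favours the claim. Loss of this kind is possible, for example if a patient with a failing shell goes to another surgeon. The documents neither show that it will happen nor exclude it.

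The numbers leave room for it to matter. The allowance covers 347 − 277 = 70 hips. Expected failures among those analysed are 277 × 0.055 ≈ 15, and an exact interval permits at most 19. The group with unknown status could therefore be several times larger than the number of failures that decides the result, and the report as planned would not show how far the conclusion depends on it.

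**Working it through.** **Inputs.** From the plan: bound 90%, expected success 94.5%, two-sided 90% interval (one-sided 5%), power 95%, 277 evaluable, 20% loss, 347 enrolled. Assumed here: the ratio k of the five-year failure rate in lost hips to that in seen hips.

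**1. The plan's own figures.** With the variance taken at the expected rate,

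n = (1.645 + 1.645)² × 0.945 × 0.055 / 0.045² = 277.8,

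against the stated 277. Then 277 / 0.8 = 346.25, rounded up to 347. Both figures reproduce.

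**2. Passing threshold at n = 277.** An exact (Clopper-Pearson) lower bound exceeds 90% with up to 19 failures; Wilson and log-log bounds give the same limit. A Wald bound allows 20.

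**3. False-claim rate under outcome-related loss.** Fix true overall failure at 10%, the null boundary. With 20% lost, the failure rate f in seen hips satisfies 0.8f + 0.2kf = 0.10, so

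f = 0.10 / (0.8 + 0.2k).

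The false-claim rate is the binomial probability of at most 19 (exact) or at most 20 (Wald) failures in 277 at rate f.

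| k | Seen hips, f | Lost hips, kf | Exact | Wald |
|---|---|---|---|---|
| 1 | 10.0% | 10.0% | 4.5% | 7.0% |
| 1.25 | 9.5% | 11.9% | 7.5% | 11.1% |
| 1.5 | 9.1% | 13.6% | 11.5% | 16.4% |
| 2 | 8.3% | 16.7% | 22.1% | 29.4% |
| 3 | 7.1% | 21.4% | 48.7% | 57.9% |

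The k = 1 row is the proper baseline for each interval, rather than the nominal 5%.

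**4. If the interval came from Kaplan-Meier.** This was simulated with 347 hips, 20% lost at times uniform over 0–5 years, and failures before loss counted. At k = 2 the false-claim rate is 10.5% (log-log) to 15.5% (linear). At k = 1 it is 4.3% to 6.9%.

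**5. Tipping point on all 347 hips.** The exact lower bound exceeds 90% with up to 25 failures in 347 (bound 90.08%) and falls below it with 26 (89.76%).

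- 15 failures in 277 (5.4%): the claim survives 25 − 15 = 10 failures among the 70 unseen (14.3%), which is 2.6 times the seen rate.
- 19 failures in 277 (6.9%): it survives 25 − 19 = 6 among the 70 (8.6%), which is 1.25 times the seen rate.

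**The case against.** **The ratio is assumed.** This is correct. No section gives a failure rate for lost hips or says that loss is related to loosening, and patients who do well may also stop attending. A reader might take the 22% at k = 2 as the trial's false-claim rate. The documents do not support that: it needs a twofold ratio, complete cases, an exact-type interval and true success of exactly 90%, whereas the plan expects 94.5%.

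**Kaplan-Meier may be what is meant.** Section 8.1.1 speaks of a survival rate and displays such a curve, so the reading is plausible, and it cuts the k = 2 figure to about 10–16%. That is still more than twice the matching k = 1 rate, because censoring also assumes that loss is unrelated to failure. The gain also depends on failures before loss being recorded: if every failure in lost hips went unseen, the same simulation gives 43% to 53%.

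**The 20% is an allowance, and the plan works to reduce loss.** This stands. Loss is declared only after three calls and a certified letter (4.3). A questionnaire covering survivorship is used through year ten when the HHS is not done (Evaluation Schedule). Operative-site events are reportable at any time (6.1), and visits may be reimbursed (13.3). Subjects also leave through death, withdrawal or centre closure, and the plan does not say whether the 20% includes these. If only half of the 20% carried a twofold risk, the average ratio among the lost would be 1.5 and the exact rate 11.5%. These measures lower the amount of loss but do not analyse what remains.

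**Section 8.3 forbids a sensitivity analysis.** A reader might infer this from the ban on imputation. The sentence does not clearly say so, and the point does not rely on it. None is planned on either reading.

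**Conclusion.** The point holds as a gap in the plan. The non-inferiority claim rests on lost hips loosening no more often than seen ones, and nothing specified tests that. Over assumed ratios of 1.25 to 3, the complete-case false-claim rate at true success of 90% runs from 7.5% to 49% (exact) or 11% to 58% (Wald), against 4.5% or 7.0% without outcome-related loss. These figures assume the full 20% is lost and that all lost hips carry the raised rate.

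It would go too far to say that the conclusion must depend on the assumption. At about the planned result, 15 failures in 277, it takes more than 2.6 times the seen failure rate among 70 unseen hips to overturn the claim. The fragility lies in narrow passes: at 19 in 277, anything above 1.25 times is enough. This is a cheap improvement to the plan and does not show that the design fails.

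**What to change.** Keep the main estimate without imputation. Add to 8.3 a pre-specified tipping-point analysis of the primary endpoint:

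- use all implanted hips, and state how many have unknown five-year status;
- add failures among those hips until the lower limit of the 90% interval reaches 90%, using the same named interval method as the primary test;
- report that number of failures and the ratio of the implied failure rate in unseen hips to the observed rate;
- describe the claim as robust only if the ratio exceeds a value that the sponsor fixes before any data are seen.

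The cost is one paragraph and one table, with no extra patients or visits. The downside for the sponsor is that a narrow pass would have to be reported as fragile.
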